7.3 Questionnaire regarding the childbirth experience

Four weeks after birth all Robson group I women at the included birth care units will receive a request to complete an online questionnaire regarding birth experience, the Childbirth Experience Questionnaire CEQ. (Appendix B).

7.4 Confidentiality

The Trial Manager shall arrange for the secure retention of the participant identification and the code list. Participant files shall be kept for the maximum period of time permitted by each birth care unit. The trial documentation shall be retained and stored during the trial and for 10 years after trial closure. All information concerning the trial will be stored in a safe place inaccessible to unauthorized personnel.

8 STATISTICAL METHODS AND DATA ANALYSIS

8.1 Determination of Sample Size

The determination of the sample size (number of clusters and individuals for analysis) is based on a power calculation with the least occurring primary outcome; emergency caesarean section, which is 9.2 % in the study population (p1). Further, we expect that the emergency caesarean section rate will be 6.9 % (p2) when using the new guideline for labour progression.

Formula (4) on page 320 in the article by Hayes et al. (24) is used to calculate the needed number of clusters and participants. According to this formula, with a chosen significance level of 0.05, a power of 80 % and p1=9.2 % and p2=6.9 %, we will have to include at least 14 clusters using the allocated guideline in 6582 Robson group I women.

All statistical analysis will be conducted in STATA, SPSS or similar statistical software.

In the 14 clusters there will be approximately 8000 women fulfilling the inclusion criteria per year (2012). With an expected inclusion of 90 % and a dropout of 10%, the required numbers of women should be included within 10-12 months.

8.2 Randomisation

8.2.1 Allocation-sequence generation

Key elements to specify regarding allocation of treatment are:

- The method of generating the allocation sequence is computer-generated
- The allocation ratio is equal to one
- The type of randomisation is restricted
- The factor; size of birth care unit and rate of emergency caesarean sections will be used for stratification

8.3 Planned analyses

The main statistical analysis is planned when all data is collected and the files are merged.

Deviation from the original statistical plan will be described and justified in the Clinical Study Report. Amendments to plan can be done until day of data base lock. The statistician will perform analysis blinded to the participant's affiliation to the groups as a control of the analysis.

8.4 Statistical Analysis

The analyses will be conducted according to the principle of intention-to-treat to estimate the effect of assigned guideline. The difference between groups will be presented with a risk ratio (RR) and a 95 % confidence interval (95% CI). For dichotomous efficacy variables a significance test taking into account the cluster structure of the data will be used (25). In the case of a substantial lack of adherence due to missing data, also 'as treated' or 'per protocol' analyses will be performed to estimate the effect of used guideline, after appropriate adjustment via inverse probability weighting or g-estimation (26,27).

9 STUDY MANAGEMENT

9.1 Investigator Delegation Procedure

The trial manager is responsible for making and updating a "delegation of tasks" with the listing of all the involved coworkers and their role in the project. The PI will ensure appropriate introduction and continuous updating, if relevant, of the study at each cluster.

9.2 Protocol Adherence

Investigators ascertain they will apply due diligence to avoid protocol deviations.

If any, significant protocol deviations will be recorded and reported in the Clinical Study Report (CSR).

9.3 Study Amendments

If the study protocol is revised, the amendment and/or a new version of the protocol (Amended Protocol) must be notified to and approved by the Competent Authority and the ethics committees according to EU and national regulations.

9.4 Audit and Inspections

Authorized representatives of a competent authority and ethics committee may visit the centres to perform inspections, including source data verification. The purpose of an inspection is to systematically and independently examine all study-related activities and documents to determine whether these activities were conducted, and data were recorded, analyzed, and accurately reported according to the protocol and any applicable regulatory requirements. The PI will ensure that the inspectors and auditors will be provided with access to source data/documents.

10 ETHICAL AND REGULATORY REQUIREMENTS

The trial will be conducted in accordance with ethical principles that have their origin in the Declaration of Helsinki and applicable regulatory requirements. Registration of individual data will be carried out in accordance with national personal data laws.

All women will be cared for in accordance with each birth care unit's normal procedures with respect to criteria for admission, attendance of a midwife, pain relief, mobilisation and nutrition.

10.1 Ethics Committee Approval

The protocol was approved by the Regional Committees for Medical Health Research Ethics in Norway (2013/1862/REK sørøst).

The PI is responsible for informing the ethics committee of any serious and unexpected adverse events and/or major amendments to the protocol as per national requirements.

10.2 Other Regulatory Approvals

The management at each birth care unit must agree to follow the protocol before commencement of the trial.

The protocol will be registered in www.clinicaltrials.gov before commencement of the study.

10.3 Informed Consent Procedure

Participants will be informed, that their medical records will be reviewed for trial purposes by authorized personnel, following strict regulations for confidentiality.

It will be emphasized that the participation is voluntary, and choosing not to participate will not prejudice her subsequent care. Documented informed consent must be obtained for all participants before including any data in the analyses. This will be done in accordance with the national and local regulatory requirements. The local coordinators are responsible for obtaining signed informed consents.

A copy of the participant information and consent will be given to the participants. The signed and dated consent forms will be filed in the Investigator Site File binder and also scanned to be part of the patient's electronic medical record at the hospitals.

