5.2.2 Baseline data

The following baseline data will be collected for each cluster:

- Number of Robson Group 1-deliveries in 2012
- The rate of emergency caesarean sections in Robson Group 1 in 2012

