5.3.1 Informed consent

All nulliparous women planning to give birth at any of the included birth care units will receive written information about the trial from the midwife in antenatal care, when called for routine ultrasound, at the ultrasound control or at the labour ward. Eligible women will be asked to sign an informed consent permitting her data to be included in the analyses and to answer a questionnaire on childbirth experience, four weeks after birth. All nulliparous women will have a trial sticker put on the antenatal record to make identification easier on admission for assessing Robson group affiliation.

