5.4 Guideline instruction and local coordinators

The PI will introduce the allocated guideline to each cluster. At each cluster, one person responsible for the trial at the specific birth care unit (local coordinator) will be designated. The local coordinator is responsible for inclusion of participants, record control of each participant and for the local implementation of the trial. The local coordinators will act as contact persons to PI, and they must report any challenges to her.

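### Only consenting women are analysed, under open unit-level allocation, and no trial-period unit counts are planned to show whether that selection differs by arm

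*Protocol*

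**What the plan says.** Section 5.3 places all Robson group I women in a participating unit under the guideline to which the unit was randomised. Consent under 5.3.1 covers use of the woman's data and the questionnaire, not her care. Section 7.1 has the web-CRF completed only for women with a signed consent, and 10.3 states: "Documented informed consent must be obtained for all participants before including any data in the analyses".

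Written information comes from the antenatal midwife, or "when called for routine ultrasound, at the ultrasound control or at the labour ward". Under 10.3 the local coordinators are responsible for obtaining the signature. Section 5.4 adds: "The local coordinator is responsible for inclusion of participants, record control of each participant and for the local implementation of the trial". The same section has the principal investigator introduce the allocated guideline to each unit, so allocation is open locally.

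Unit-level totals appear only in 5.2.2 and only for 2012: the number of Robson group I deliveries and "The rate of emergency caesarean sections in Robson Group 1 in 2012".

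Section 8.4 analyses by assigned guideline. It provides for additional as-treated or per-protocol analyses on this condition: "In the case of a substantial lack of adherence due to missing data".

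**The concern.** Units are randomised, but whether a treated woman enters the dataset is settled afterwards, by her consent and by a coordinator who knows the arm and also checks eligibility before data entry (7.2). No readable passage requires the signature before delivery, so the mode of delivery, which is the primary endpoint, could be known by then. Analysing by assigned guideline does not protect against this, because the women left out are not in the data.

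If women with a caesarean are approached, or agree, at different rates in the two arms, the comparison carries a selection effect that looks like a guideline effect. The list in 10.4 covers included participants only, and the readable text plans no count of eligible, non-consenting or missed women during the trial. The provision in 8.4 does not help: as-treated and per-protocol analyses, even with weighting or g-estimation, use the same consenting women.

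**Working it through.** **Inputs.** From 8.1: "with a chosen significance level of 0.05, a power of 80 % and p1=9.2 % and p2=6.9" per cent, a target of 9.2 − 6.9 = 2.3 points (risk ratio 6.9/9.2 = 0.75); 6582 women; about 8000 eligible per year; 90% inclusion; 10% dropout. The gap in caesarean rate among women not analysed is not in the documents. It is an assumption, shown as a range.

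**The plan's own accrual figure.** 8000 × 0.9 = 7200 included per year, and 7200 × 0.9 = 6480 after dropout. Then 6582/7200 × 12 = 11.0 months without dropout and 6582/6480 × 12 = 12.2 months with it, against 10–12 months stated. Dropout is not defined, so two missing fractions are carried: 10% (non-inclusion only) and 1 − 0.81 = 19% (both).

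**Formula.** Let *D* be the true control-minus-intervention difference in all eligible women, *g* the same difference among women not analysed, and *f* the fraction not analysed, equal in both arms. The overall rate is (1 − f) × analysed rate + f × missing rate, so:

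- observed difference = (D − f·g)/(1 − f)
- bias = f·(D − g)/(1 − f)

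**No true effect (D = 0).** The size of the bias is f·g/(1 − f):

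| Gap g | f = 10% | f = 19% |
|---|---|---|
| 0 | 0 | 0 |
| 5 points | 0.10 × 5/0.90 = 0.56 (24% of 2.3) | 0.19 × 5/0.81 = 1.17 (51%) |
| 10 points | 1.11 (48%) | 2.35 (102%) |

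The sign depends on which arm's missing women have the higher rate.

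**Planned effect true (D = 2.3).**

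- g = 2.3: no bias.
- g = 5: 0.111 × (2.3 − 5) = −0.30 points at f = 10%; 0.235 × (2.3 − 5) = −0.63 points at f = 19% (28% of target).
- g = −5: 0.111 × 7.3 = +0.81 points at 10%; 0.235 × 7.3 = +1.71 points at 19%.

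**Unequal inclusion, no true effect.** Take 9.2% in both arms, with share *s* analysed and missing women's rate *q* times that of analysed women. The analysed rate is 9.2/(s + (1 − s)q).

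- 70% v 90% analysed, q = 1.5: 9.2/1.15 = 8.00 v 9.2/1.05 = 8.76, a difference of 0.76 points (risk ratio 0.913).
- 70% v 90%, q = 2: 9.2/1.30 = 7.08 v 9.2/1.10 = 8.36, a difference of 1.29 points (risk ratio 0.846).
- 80% v 90%: 0.40 points at q = 1.5 and 0.70 points at q = 2.
- 81% in both arms with the same q: risk ratio 1.00.

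**What two unit totals would give.** With N eligible deliveries and C caesareans per unit, and n and c among analysed women, the rate in women not analysed is (C − c)/(N − n). That estimates the unknown *g* directly. For the trial period, N and C are not planned.

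**The case against.** The strongest reply is that consent after allocation is inherent when units are randomised before women present. Section 4.1 justifies the design by contamination, the consent route is the same in both arms, and equal selection gives no bias. All of that stands: the documents show a risk, not a bias.

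Some stronger readings are not supported:

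- A reader might infer that 8.4 replaces intention-to-treat with an as-treated analysis when data are missing. It does not; those analyses are additional and adjusted.
- A reader might infer that missing data are addressed nowhere else. Section 7.2 requires reasons for omitted assessments to be registered, and an analysis plan not seen here may say more.
- A reader might infer that consent after delivery is planned. No passage describes it; the point is only that none excludes it. Forms are dated (10.3), so timing can largely be recovered.
- A reader might take the 102% entry as the likely size. A 10-point gap is extreme beside overall rates of 7–9%, and that entry assumes no true effect and counts all dropout as missing.

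Information also comes partly from antenatal staff, which dilutes the coordinator's influence although the signature remains the coordinator's task. Section 4.1 commits to CONSORT for cluster trials, which may prompt flow reporting. Appendix C and the text between 2.2 and 3.2 could not be read. Baseline characteristics (5.3.2) allow included women to be compared by arm, but say nothing about caesareans among those left out. An analysis plan cannot supply counts that nobody collects.

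**Conclusion.** The concern holds as a checkable weakness, not as a demonstrated error. The primary comparison uses a subset selected after open allocation, with 10% to 19% of eligible women absent on the plan's own figures. Assuming no true effect, a 5-point between-arm gap among them would produce about 0.6 to 1.2 points of spurious difference against the 2.3-point target. With no gap there is no bias. The gap is an assumption, and the readable text plans no trial-period data to estimate it. Separately, the condition in 8.4 confuses non-adherence with missing data, and the analyses it triggers do not address non-inclusion. The remedy is cheap enough that the plan should adopt it.

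**What to change.** 1. In 5.2.2, collect for the study period the same two aggregate figures per unit as for 2012: Robson group I deliveries and the emergency caesareans among them.
2. Report eligible, consenting and analysed numbers by unit and arm.
3. Pre-specify a cluster-level intention-to-treat sensitivity analysis of the primary endpoint on all eligible women, reported beside the main result.
4. Tabulate consent date against delivery date from the dated forms.
5. Reword 8.4 so that per-protocol or as-treated analysis is triggered by measured non-adherence (compliance is already registered under 2.2). Handle missing data among consenting women within intention-to-treat.

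Weighting for non-consenting women is not proposed, because it needs individual data that 7.1 and 10.3 exclude.

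The cost is two aggregate figures per unit, some tabulation, and an amendment, which 9.3 requires to be approved and not merely notified. That submission should include agreement that aggregate counts may be used without individual consent, given the wording of 10.3. Care and sample size do not change. One limit remains: the totals must cover the same period and use the same Robson group I classification as the trial data.

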10.4 Subject Identification

The local coordinators are responsible for keeping a list of all included participants including date of birth and personal number, full names and last known addresses.

The participants will be identified in the web-CRF by inclusion numbers.

11 TRIAL SPONSORSHIP AND FINANCING

Financing of a one year postdoctoral position is granted from the Østfold Hospital trust. Additional financing for a two years postdoctoral position (2015 – 2016) and a three year PhD position will be applied for at the South-Eastern Norway Regional Health Authority.

12 TRIAL INSURANCE

Participants are covered by the Norwegian Patient Compensation System.

13 PUBLICATION POLICY

All colleagues, who have contributed significantly with the planning and/or performance of the study (Vancouver convention 1988), may be included in the list of authors.

Preliminary planned publications:

- Paper 1: The Labour Progression study, evaluating the use of a new partogram in labour care for low-risk nulliparous women. A protocol of a cluster randomised trial in Norway
- Paper 2: Is it possible to reduce the rate of emergency cesarean section in low-risk nulliparous without compromising maternal and fetal health? A cluster randomised trial
- Paper 3: Is it possible to reduce the rate of augmentation in low-risk nulliparous without compromising maternal and fetal health? - A cluster randomised trial
- Paper 4: How does the amount of oxytocin during labour affect the outcome in neonates? A cohort of low-risk nulliparous women
- Paper 5: The use of oxytocin and labour progression in obese women.— A cohort of low-risk nulliparous women
- Paper 6: Does the expected labour progression according to contemporary research, correlate with labour progression in low-risk nulliparous women? A cohort of low-risk nulliparous women
- Paper 7: Low-risk nulliparous women's childbirth experience labour according to two guidelines for expected progression of labour A cluster randomised trial

Ownership and use of data:

The ownership of the data generated at each unit belongs to each of the included hospitals. The project group has managerial prerogative over the data entered into the web based case report form, designed for this study. The managerial prerogative is not in hindrance with each hospital's right to publish their own data after

publication of planned articles, provided that it is not in conflict with planned publications. Provided that the criteria for authorship is fulfilled, according to the International Committee of Medical Journal Editors (ICMJE), one author from each hospital is invited to participate as co author of one of the planned publications.

15 LIST OF APPENDICES

- 15.1 Appendix A Zhang's curve for progression of labour included instructions
- 15.2 Appendix B- Questionnaire for childbirth experience, No
- 15.3 Appendix C Flow chart of inclusion
- 15.4 Appendix D Request for participation in a research project
- 15.5 Appendix E Information on web-CRF, NTNU

Additional information to the Protocol.

Additional information to Figure 1, page 7:

The medications Demerol and Scopolamin are administrated at time point in labour indicated by the arrows in the curve.

Demerol is a synthetic opioid. Scopolamin is a hyoscine, often used against nausea.
